21. Significant acute or chronic medical, neurological, or psychiatric illness that, in the judgment of the investigator, could compromise subject safety, limit the subject's ability to complete the study, and/or compromise the objectives of the study;
22. Previous clinical trial participation for the indication being treated in this protocol.

Dose Regimen/Route- Duration of Treatment and Follow up:

Part A

Subjects will be assigned by the local clinician to receive topical administration of either 0.03% BMX-010 or 0.1% BMX-010, to apply to Acne Vulgaris on the face. Topical therapy with BMX-010 will be either QD or BID as assigned by the local clinician. The planned treatment duration is a minimum of 7 days and a maximum of 28 days. Completion of 28 days of treatment will be recommended to all subjects; however, subjects who have full clearing of the Acne Vulgaris, as determined by the clinical center investigator, may stop study drug therapy and remain in the study with a final evaluation at Day 29 or Day 43 (at the discretion of the investigator).

Part B

Subjects will be randomized 2:1 to receive topical administration of BMX-010 or Placebo which will be dosed at the concentration, formulation, and frequency as defined by Part A. Study product will be applied liberally to Acne Vulgaris on the face. The planned treatment duration is a minimum of 7 days and a maximum of 28 days. Completion of 28 days of treatment will be recommended to all subjects; however, subjects who have full clearing of the Acne Vulgaris, as determined by the clinical center investigator, may stop therapy and remain in the study with a final evaluation at Day 29 or Day 43 at the discretion of the investigator. There will be weekly visits with follow-up done at approximately Days 8, 15, 22, 29 and 43.

Dosage Form and Strength Formulation:

BMX-010

BMX-010 will be supplied at concentrations of 0.03% and 0.1%. BMX-010 will be manufactured by Albany Molecular Research, Inc. (AMRI), and formulation and packaging is done by Velesco Pharmaceutical Services, LLC. BMX-010 is yellow/brown in color and transient (up to 7 days) of yellow discoloration of skin can occur. BMX-010 is dispensed in approximately 10 mL tubes.

Placebo

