6 STUDY OBJECTIVES

6.1 Primary Objectives

Part A

1. Determine whether the optimum frequency of topical application of BMX-010 0.03% is once per day or twice per day for a treatment interval of 7 to 28 days.
2. Determine whether the optimum frequency of topical application of BMX-010 0.1% is once per day or twice per day for a treatment interval of 7 to 28 days.
3. Determine if BMX-010 cream or gel provides better efficacy.
4. Evaluate the efficacy of BMX-010 0.03% in treatment of Acne Vulgaris.
5. Evaluate the efficacy of BMX-010 0.1% in treatment of Acne Vulgaris.

Part B

1. Evaluate the efficacy of BMX-010 compared to placebo in a randomized, double-blind trial.
2. Determine the percent of subjects showing a 2 grade improvement in IGA score after treatment with BMX-010 compared to Placebo.
3. Determine the percent of subjects showing a 2 grade improvement in IGA score with full or partial clearing (final IGA score of 1 or 0) after treatment with BMX-010 compared to Placebo.
4. Determine the time to full clearing of Acne Vulgaris after initiation of treatment with BMX-010.

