7.2 Part B Study Design

Subjects will be randomized 2:1 to receive topical administration of BMX-010 or Placebo which will be dosed at the concentration, formulation, and frequency as defined by Part A. Study product will be applied liberally to Acne Vulgaris on the face. The planned treatment duration is a minimum of 7 days and a maximum of 28 days. Completion of 28 days of treatment will be recommended to all subjects; however, subjects who have full clearing of the Acne Vulgaris, as determined by the clinical center investigator, may stop therapy and remain in the study with a final evaluation at Day 29 or Day 43 at the discretion of the investigator. There will be weekly visits with follow-up done at approximately Days 8, 15, 22, 29 and 43.

Figure 7.a Study Design for both parts

Following written informed consent, subjects will undergo screening evaluations within 14 days prior to the first application of study drug. The screening evaluations will include complete medical history, complete physical examination (including vital signs, weight, and height), clinical laboratory evaluations, urine pregnancy test for females of child-bearing potential (a negative pregnancy test is required within 48 hours prior to the start of drug treatment), concurrent medical conditions, and concomitant medication assessments.

Subjects will be scored by the clinician for IGA. The clinician will also obtain counts of the inflammatory and noninflammatory lesions on the face.

The subject will be asked a series of Patient Reported Outcomes (Appendix A).

In **Part A**, all eligible Subjects enrolled will receive the active study drug, BMX-010. Subjects will treat their Acne Vulgaris on the face with the study product. This will be demonstrated at the Baseline visit. Subjects will be instructed by the clinical center staff and informed how often they should dose each day (QD or BID).

In **Part B**, all eligible Subjects enrolled will be randomized to the study drug (BMX-010) or Placebo. Subjects will treat their Acne Vulgaris on the face with the study product. This will be demonstrated at the Baseline visit. Subjects will be instructed by the clinical center staff and informed how often they should dose each day, which will have been confirmed by Part A of the study.

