7.2.1 Stopping Rules

The following stopping criteria will be implemented:

1. Subject stopping criteria: If a subject experiences an AE that is deemed by the clinical center Principal Investigator to be at least “possibly” drug-related and is Grade ≥ 2 in severity (using the Common Terminology Criteria for Adverse Events (CTCAE v 5), that subject will be withdrawn from dosing, return for all scheduled evaluation visits, and be followed until the AE resolves or stabilizes.

2. Cohort stopping criteria: If 1 subject in a cohort experiences an AE that is deemed by the clinical center Principal Investigator to be probably or definitely drug-related and is Grade ≥ 3 in severity by CTCAE, or if 2 subjects in a cohort experience AEs that are deemed by the clinical center Principal Investigator(s) to be at least “possibly” drug-related and are Grade $>/= 3$ in severity by CTCAE, dosing further subjects will be suspended until data is reviewed by the sponsor.
3. Dose stopping criteria: If the Acne Vulgaris is deemed as cleared by the study investigator (IGA=0), the subject will be instructed to stop dosing or continue based on the discretion of the clinical center investigator. Acne Vulgaris should be considered clear if it is not showing any inflammatory signs of disease. If it is decided by the local investigator to stop drug treatment, the clinical center investigator will determine which of the following scenarios will be implemented :
 - The subject should return to the clinical center weekly for further assessment.
 - The subject should return the following week to complete the end of study (Day 43) follow up visit.

If the subject is still in the study, and the Acne Vulgaris returns, the subject should contact the clinical center and resume treatment (through Day 28) and weekly visits until the planned Day 43.

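### Part B: early clearers may have their Day 43 visit one week after clearing, so some can have no IGA or lesion count at Day 29 or Day 43

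*Protocol*

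**What the plan says.** Two places describe what happens to a Part B subject who clears fully and stops treatment. In the Synopsis (Dose Regimen, Part B) such subjects "may stop therapy and remain in the study with a final evaluation at Day 29 or Day 43 at the discretion of the investigator". Section 7.2 has them "remain in the study with a final evaluation at Day 29 or Day 43 at the discretion of the investigator", and adds: "There will be weekly visits with follow-up done at approximately Days 8, 15, 22, 29 and 43".

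Section 7.2.1, item 3, which sits under Part B, gives the investigator two choices once dosing stops, with no criterion for choosing. One is "The subject should return to the clinical center weekly for further assessment". The other is "The subject should return the following week to complete the end of study (Day 43) follow up visit". The clause on recurrence that follows opens "If the subject is still in the study, and the Acne Vulgaris returns", so it does not reach anyone who has already completed the study. Item 1 of the same section treats subjects taken off drug for an adverse event differently: "that subject will be withdrawn from dosing, return for all scheduled evaluation visits, and be followed until the AE resolves or stabilizes".

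Table 4.a schedules IGA and facial lesion counts at Days 8, 15, 22, 29 and 43, each within 2 days. Several efficacy measures are tied to the last visit rather than to a named day. The third Part B primary objective (section 6.1) requires "full or partial clearing (final IGA score of 1 or 0"). Section 6.2 takes lesion counts to the end of the study, and section 11.1 takes IGA change to the final follow-up visit.

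**The concern.** A site cannot follow both rules for a subject who clears at Day 8 or Day 15. If it takes the one-week option, the visit is recorded as Day 43 although it takes place weeks earlier, and the label hides the mistiming.

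The affected subjects matter for the primary comparison. Entry requires a baseline IGA of at least 2 (section 8.1), and section 7.2.1 defines clearing as IGA 0. Every clearer has therefore improved by at least two grades and meets the third primary objective at that moment. If the end-of-study visit follows a week later, the final score is fixed then. Other subjects are scored at Day 43, about two weeks after planned dosing ends. Assessment time thus depends on outcome. If the arms clear at different rates, the comparison with placebo mixes assessment days in different proportions.

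Relapse after an early exit leaves no IGA or lesion count. The only later contact is the optional call or mailing at 1, 2 and/or 3 months (section 11.3, Appendix B). It asks a general question about current status, which may reveal some relapses but is not an endpoint assessment. An SAP can define how to handle a missing visit, but it cannot supply an observation that the protocol allowed a site not to make.

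**Working it through.** The protocol states no figure on this point, so there is nothing to reproduce. The check is calendar arithmetic followed by an illustration on assumed rates.

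**Calendar.** Inputs: visit days from section 7.2; windows of 2 days either side from Table 4.a, so Day 29 means Days 27-31 and Day 43 means Days 41-45; one week taken as 7 days.

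| Clears at | Exit, nominal | Exit, clearing visit within window | Day 29 value? | Day 43 value? |
|---|---|---|---|---|
| Day 8 | 8 + 7 = 15 | 13-17 | no | no |
| Day 15 | 15 + 7 = 22 | 20-24 | no | no |
| Day 22 | 22 + 7 = 29 | 27-31 | yes | no |

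Allowing the exit visit its own 2 days as well, the latest exit for a Day 15 clearer is 15 + 2 + 7 + 2 = Day 26, one day before the Day 29 window opens. If the following week is stretched to 13 days, a late Day 15 clearer could reach 15 + 2 + 13 = Day 30, but a Day 8 clearer still reaches only 8 + 2 + 13 = Day 23.

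Subjects dosed to Day 28 (Table 4.a, footnote 8) are scored at Day 43 after 41 - 28 = 13 to 45 - 28 = 17 days off drug.

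**Illustration against a common Day 43.** Every rate here is an assumption. Let p be the proportion who clear, e the share of clearers who take the one-week exit (the same in both arms), and d the extra proportion of those subjects who lose response by Day 43 compared with one week after clearing, net of any resumed treatment. A and P denote active and placebo.

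Overstatement in points = 100 × e × (pA × dA - pP × dP)

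Take pA = 0.20 and pP = 0.05, on the planned maximum of 100 v 50 subjects (section 9.1.1), with d equal in both arms:

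- e = 0.5, d = 0.20: 100 × 0.5 × 0.15 × 0.20 = 1.5 points.
- e = 1 (a ceiling), d = 0.40: 100 × 1 × 0.15 × 0.40 = 6.0 points.
- In counts over that range, 10-20 active and 1.25-2.5 placebo subjects leave early. Of these, 2-8 active (2-8%) and 0.25-1 placebo (0.5-2%) count as final-score responders but would not be responders at Day 43.
- e = 0.1: 100 × 0.1 × 0.15 × 0.20 = 0.3 to 100 × 0.1 × 0.15 × 0.40 = 0.6 points.

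If the extra loss on placebo is twice that on active:

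- e = 0.5: 100 × 0.5 × (0.20 × 0.20 - 0.05 × 0.40) = 1 point.
- e = 1: 100 × 1 × (0.20 × 0.40 - 0.05 × 0.80) = 4 points.

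The sign reverses once dP/dA exceeds pA/pP. That threshold is 0.20/0.05 = 4 here, but only 0.10/0.08 = 1.25 if 10% v 8% clear.

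The illustration counts all clearers, including those at Day 22, because all who take this exit lack Day 43. It says nothing about the size of any bias against Day 29.

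**The case against.** The gap is a permitted path, not the default. The protocol recommends 28 days of treatment to everyone. An early exit needs a score of 0, a decision to stop despite that recommendation, and the choice of the one-week return over weekly visits. Nothing in the document supports an exit share of 50% or more, and at 10% the illustrated overstatement is well under one point. This stands, and the range in the conclusion includes it. It limits the likely size but does not remove the contradiction.

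Endpoint definitions may properly sit in the SAP (section 14). The second primary objective names no day, and time to full clearing is unaffected. That also stands. What remains for the protocol is that the observation itself is not guaranteed.

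A common Day 43 does not equalize time off drug. A subject who stopped at Day 8 would be scored about 43 - 8 = 35 days after stopping, against 13-17 days for subjects dosed to Day 28. This is true, but a fixed calendar day from randomization makes assessment time independent of response, which the one-week exit does not.

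The contrast with adverse-event withdrawals is weak as an argument about efficacy, since that follow-up serves safety. It shows only that keeping subjects on schedule while off drug is already considered workable.

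**Conclusion.** The point holds and should be fixed. The Synopsis and section 7.2 conflict with section 7.2.1, and nothing else in the protocol resolves the conflict. On the ordinary 7-day reading, Day 8 and Day 15 clearers who take the one-week exit have no IGA or lesion count at either Day 29 or Day 43. Day 22 clearers who take it have Day 29 only, and the Day 29 option in section 7.2 likewise leaves Day 43 unguaranteed.

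Confidence is high for the contradiction and the missed visits. The size and direction of any bias cannot be derived from the protocol, which gives no clearing, exit or relapse rates. With 20% v 5% clearing and equal extra loss of 20-40 points, the overstatement against Day 43 runs from 0.3 points (10% exit share) to 6 points (100%). Greater relapse on placebo reduces or reverses it.

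The trial is exploratory and its size has no statistical basis (section 14.6), which limits the consequence. Part B is nevertheless meant to inform the planning of later studies, so a final responder rate with response-dependent timing would carry forward.

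**What to change.** Reconcile the Synopsis, section 7.2 and section 7.2.1 so that they give one follow-up rule for Part B subjects who clear. Section 7.1 has the same Day 29 or Day 43 wording for Part A and should be read alongside if section 7.2.1 is meant to apply there.

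Tie the Part B IGA responder and lesion-count endpoints to one scheduled visit day. The detailed definition can go in the SAP, but the protocol must guarantee the visit. Have every randomized subject attend the Day 29 and Day 43 assessments already in Table 4.a, whatever their clearing or dosing status.

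This concerns outcome assessment. The provisions on dosing, stopping and resumption are for the sponsor to reconcile. They must be read together with the change, because some subjects who would have left early will still be in the study when acne returns and will then come under the resumption clause. The remaining cost is protocol wording and a few already scheduled visits for early clearers.

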8 SELECTION AND WITHDRAWAL OF SUBJECTS

8.1 Inclusion Criteria

1. Male or female, at least 18 years of age;
2. A clinical diagnosis of mild to severe facial Acne Vulgaris; Subjects may also have acne at other body sites;
3. Screening and Baseline IGA score ≥ 2 (greater than or equal to 2);
4. Willing to refrain from using any topical or systemic treatments for inflammatory skin disease, other than the investigational product;
5. Candidate for topical treatment of Acne;
6. If a cleanser, moisturizer or sunscreen is needed during the study, Subjects must be willing to use only allowed cleansers, moisturizers, sunscreens, or moisturizer/sunscreen combination products. If the subject wears makeup they must agree to use non-comedogenic makeup.
7. Females of child-bearing potential must have a negative urine pregnancy test within 48 hours prior to the first drug administration;
8. Females of child-bearing potential must be willing to use 2 methods of contraception deemed adequate by the investigator (for example, oral contraceptive pills plus a barrier method) through the trial and for 1 month thereafter to be eligible for, and continue participation in, the study;
9. Ability to complete the study in compliance with the protocol, including agreement in writing to apply study product only to the assigned areas; and
10. Ability to understand and provide written informed consent.

8.2 Exclusion Criteria:

1. Any underlying disease(s) or some other dermatological condition of the face that requires the use of interfering topical or systemic therapy or makes evaluations and lesion count inconclusive;
2. Use of androgen receptor blockers (such as spironolactone or flutamide);
3. Severe cystic acne, acne conglobata, acne fulminans, or secondary acne;
4. Use of phototherapy devices, energy-based devices, adhesive cleansing strips, or cosmetic procedures (e.g., facials, peeling, comedo extraction) in the past week;
5. Presence of beard or excessive facial hair at Screening which would interfere with the study treatments or study assessments and refusal to remove for duration of study;
6. Prior or current concomitant therapies that would interfere with assessments in the study;
7. Subjects with any underlying disease that the Investigator deems uncontrolled, and poses a concern for the subject's safety while participating in the study;
8. Use of anti-inflammatory medications, salicylic acid; corticosteroids, antibiotics, antibacterials (including benzoyl peroxide-containing products [e.g., benzamycin]), retinoids; other topical acne treatments (e.g., photodynamic therapy, medicated soaps such as those containing benzoyl peroxide, salicylic acid, sulfur, or sodium sulfacetamide) in the past 2 weeks;

9. Oral retinoid use (e.g., isotretinoin) within 6 months prior to baseline or vitamin A supplements greater than 10,000 units/day within 6 months of baseline;
10. Concomitant skin disease that could confound clinical evaluations or increase risk to the subject;
11. Use of medicated make-up (including anti-aging make-up) throughout the study;
12. Use during the study of 1) systemic steroids, 2) topical retinoids to the face, 3) antibiotics known to impact acne, 4) immunosuppressive agents, or immunomodulators;
13. Facial use of 1) topical steroids, 2) topical anti-inflammatory agents, 3) topical antimycotics, 4) any topical acne treatments or 4) topical antibiotics;
14. Use of medicated cleansers on the face (throughout the study);
15. Use of topical astringents or abrasives, medical topical preparations (prescription and OTC products) within 2 days prior to Baseline and throughout the study;
16. Systemic or skin infection requiring antimicrobial therapy;
17. Systemic chemotherapy or radiotherapy within 4 weeks of the Baseline Visit;
18. Immunocompromise of any cause, known human immunodeficiency virus infection, or acquired immunodeficiency syndrome;
19. Pregnancy, planned pregnancy, lactation, or inadequate contraception as judged by the investigator;
20. Active drug or alcohol dependence;
21. Significant acute or chronic medical, neurological, or psychiatric illness that, in the judgment of the investigator, could compromise subject safety, limit the subject's ability to complete the study, and/or compromise the objectives of the study;
22. Previous clinical trial participation for the indication being treated in this protocol.

8.3 Criteria for Discontinuation or Withdrawal of a Subject

All subjects are free to withdraw from study participation at any time, for any reason, and without prejudice to their further medical care. In addition, the investigator may terminate a subject from the study at any time. The primary reason for discontinuation should be recorded on the case report form (CRF) using one of the following categories:

1. Adverse event. The subject experiences an AE that imposes an unacceptable risk to the subject's health, or the subject is unwilling to continue because of an AE.
2. Lack of therapeutic effect. The investigator has determined that study drug administration is not benefitting the subject, and continued participation poses an unacceptable risk to the subject.
3. Inclusion/exclusion criteria violation. The investigator discovers that the subject did not meet all of the inclusion/exclusion criteria after study enrollment.
4. Protocol noncompliance. The subject has a significant protocol deviation, does not comply with study drug administration schedule, or fails to adhere to other study requirements as stated in the protocol.
5. Lost to follow-up. The subject does not return to the clinic for scheduled assessments, and does not respond to the site's attempts to contact the subject.
6. Voluntary withdrawal. The subject wishes to withdraw from the study. The clinical center should attempt to determine the underlying reason for the voluntary withdrawal and document it on the CRF; if the underlying reason is documented as an AE or lack of

efficacy, the category of withdrawal should be marked in the corresponding category and not as voluntary withdrawal.

7. Study termination. The sponsor, Institutional Review Board (IRB), or regulatory agency terminates the study.
8. Pregnancy.
9. Other. Any reason that does not fall into 1 of the above categories. The specific reason should be recorded on the CRF.

Following early discontinuation from the study, the subject will be informed regarding the additional study evaluations that are necessary to monitor his/her safety. These subjects will be encouraged to participate in the final follow up study visit.

In order to meet the number of specified evaluable subjects, a discontinued or withdrawn subject may be replaced and the newly enrolled subject will be assigned the identical treatment of the withdrawn subject.

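### Section 8.3 does not separate stopping study drug from leaving the study, so assessable Part B IGA and lesion-count data may be lost for reasons related to outcome or arm

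*Protocol*

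**What the plan says.** Section 8.3 gives one list of reasons for discontinuation, to be recorded on the CRF. Four of them need not mean that the subject can no longer be assessed:

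- The first category, for adverse events, reads: "The subject experiences an AE that imposes an unacceptable risk to the subject's health, or the subject is unwilling to continue because of an AE".
- The second category, for lack of effect, reads: "The investigator has determined that study drug administration is not benefitting the subject, and continued participation poses an unacceptable risk to the subject".
- The third category, for ineligibility, reads: "The investigator discovers that the subject did not meet all of the inclusion/exclusion criteria after study enrollment".
- Non-compliance, which includes a subject who "does not comply with study drug administration schedule, or fails to adhere to other study requirements as stated in the protocol".

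The same list holds loss to follow-up and voluntary withdrawal. A voluntary withdrawal whose underlying reason is an adverse event or lack of efficacy is recoded to that reason.

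On what follows, 8.3 says: "Following early discontinuation from the study, the subject will be informed regarding the additional study evaluations that are necessary to monitor his/her safety". It then adds: "These subjects will be encouraged to participate in the final follow up study visit". A leaver may also be replaced: "a discontinued or withdrawn subject may be replaced and the newly enrolled subject will be assigned the identical treatment of the withdrawn subject".

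Section 7.2.1 handles one kind of drug stop differently. For an at least possibly related adverse event of Grade 2 or higher, "that subject will be withdrawn from dosing, return for all scheduled evaluation visits, and be followed until the AE resolves or stabilizes". For a subject who stops because the acne has cleared, it lets the investigator choose between weekly returns and an end-of-study visit the following week.

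Table 4.a schedules IGA and lesion counts at Days 8, 15, 22, 29 and 43. It has no early-termination column, although the abbreviation for early termination is in the list in section 3.

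**The concern.** Stopping a topical product does not prevent an investigator from grading a face. Section 7.2.1 recognises this for related adverse events; section 8.3 does not make the distinction for any reason. Two consequences follow.

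First, a subject who stops drug for a related adverse event can be read as falling under either section, and the two lead to different amounts of efficacy data.

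Second, for lack of effect, non-compliance and late-found ineligibility, no other passage keeps the subject on the visits. Leaving for lack of effect is related to outcome by definition. Leaving for adverse events can be related to arm: section 10.2 expects skin irritation from BMX-010 in under 10% of subjects and discoloration in over 30%.

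At stake are the Part B primary objectives: the randomized comparisons of 2-grade IGA improvement and of improvement to IGA 0 or 1, and the time to full clearing, which relies on weekly assessments. Missing-data methods belong in the SAP, but which visits are required after drug stops is settled here.

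**Working it through.** **No stated figure to reproduce.** Section 14.6 says the sample size has no statistical basis, and no response or dropout rate is given. The allocation is consistent: 150 at 2:1 is 100 and 50, as in section 9.1.1.

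**Step 1. The rules side by side.**

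| | 7.2.1, subject stopping rule | 8.3 |
|---|---|---|
| Trigger | Adverse event at least possibly related, Grade 2 or higher | Adverse event of unacceptable risk, or subject unwilling to go on; also lack of effect, ineligibility, non-compliance |
| What ends | Dosing | Study participation |
| Visits afterwards | All scheduled | Safety evaluations; final visit encouraged |

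**Step 2. One subject under both.** Take drug stopped on Day 10 for related Grade 2 irritation, with the subject unwilling to continue. Under 7.2.1, IGA and lesion counts follow at Days 15, 22, 29 and 43: four assessments. Under 8.3 there are none or one. So three or four are lost.

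**Step 3. Time to full clearing.** If that subject attends only Day 43, the gap between assessments runs from Day 8 to Day 43, which is 43 − 8 = 35 days. On the full schedule the gaps are 7 days up to Day 29 and then 14.

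**Step 4. Analysis set.** Section 14.1 requires at least one post-baseline visit. A randomized subject who leaves before the Day 8 visit and does not attend the final visit drops out of the efficacy set and may be replaced.

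**Step 5. Illustration, true effect present.** Assumptions: 100 v 50 subjects, true response 30% v 20% (30 and 10 responders), all leavers non-responders, response calculated among those observed.

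| Assumed leavers (active / placebo) | Observed rates | Difference |
|---|---|---|
| 0 / 0 | 30/100 v 10/50 = 30.0% v 20.0% | 10.0 |
| 10 / 10 | 30/90 v 10/40 = 33.3% v 25.0% | 8.3 |
| 15 / 1 | 30/85 v 10/49 = 35.3% v 20.4% | 14.9 |

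**Step 6. Illustration, no true effect.** If a share l of non-responders leaves, the observed rate is p / (p + (1 − p)(1 − l)). With p = 20% in both arms and l = 5% active, 20% placebo: 0.20/0.96 − 0.20/0.84 = 20.8% − 23.8% = −3.0 points. For p = 10% and 30% the same losses give −1.7 and −3.8. With l = 10% v 30% the three values (p = 10%, 20%, 30%) are −2.7, −4.6 and −5.7. Swapping the 5% and 20% losses between the arms reverses the sign.

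**Step 7. What the data alone can say.** Without assuming leavers' outcomes, the range for the difference has a width equal to the sum of the missing fractions. For 10 / 10 leavers, active lies between 30/100 and 40/100 and placebo between 10/50 and 20/50. The difference therefore lies between 30 − 40 = −10 and 40 − 20 = +20, a width of 30 points (10% + 20%).

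**The case against.** The case for leaving the text alone has real force.

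- **The sections can be read together.** 7.2.1 concerns dosing and 8.3 concerns participation, and 8.3 never states that stopping drug means leaving. A reader might infer that every drug stop becomes a study exit. The text does not support that: the investigator may terminate a subject but need not, and lack of effect as a reason also requires an unacceptable risk from continuing, which should be uncommon in a topical trial of at most 28 days. What remains is that 8.3 never says the opposite either, and that its recoding of voluntary withdrawals mixes subjects who chose to leave with those whom an investigator stopped.
- **The encouraged visit collects the endpoint.** The final clinic visit is Day 43, with IGA and lesion counts, and a subject who leaves after Day 8 normally has at least one earlier IGA. This stands, so it would be wrong to say that outcomes are certain to be lost. The weekly data between leaving and Day 43 still go.
- **Analysis may repair it.** A reader might infer that no analysis could. The figures in Step 5 show otherwise: counting leavers as non-responders gives 30/100 v 10/50, exactly 10 points, in both scenarios. The distortion there comes from an observed-case analysis that the protocol does not specify. The repair is exact only because the illustration makes every leaver a non-responder. Step 7 shows how wide the range is without that assumption.
- **The 14.9-point scenario is strained.** It loses 15% of the active arm to adverse events, while section 10.2 expects irritation in under 10%, transient discoloration is not counted as an adverse event (sections 9.2.2.1 and 9.2.3.1), and related Grade 2 events are those that 7.2.1 retains.
- **The shifts are small against the noise.** At 30% v 20% the standard error is √(0.30 × 0.70/100 + 0.20 × 0.80/50) = 7.3 points, so shifts of −1.7 and +4.9 are below one standard error in a trial meant to inform later studies.

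**Conclusion.** The point holds as a weakness in how follow-up is specified, not as demonstrated bias. Section 8.3 fails to separate stopping drug from leaving the study, overlaps with 7.2.1 on adverse events, and leaves subjects who could still be assessed with no required efficacy visit. Part B IGA and lesion counts, and the weekly data for time to full clearing, may be lost for reasons related to outcome or arm.

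Size and direction cannot be derived from the protocol. The illustrated shifts, about 2 to 6 points either way, rest on assumed response and loss rates, on leavers being non-responders, and on an observed-case analysis; they are not estimates for this trial. Because Part B is exploratory and the sample size has no statistical basis, this is a should-fix item. The reason to act is that a missed examination cannot be made up later and the remedy is cheap.

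**What to change.** 1. Reconcile 7.2.1 and 8.3 so that one rule governs follow-up after drug is stopped for an adverse event. The second clearing option in 7.2.1 (end-of-study visit the following week) should be aligned with item 3 or expressly exempted from it.
2. In 8.3 and on the CRF disposition page, record stopping study drug and withdrawing from the study as separate events, each with its own reason and date.
3. State that a Part B subject who stops drug for any reason other than withdrawal of consent remains on the Table 4.a IGA, lesion-count and adverse-event assessments through Day 43.
4. For a subject who withdraws, obtain IGA and lesion counts at the last contact if the subject agrees, and show this in Table 4.a.

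None of this changes when dosing stops or who decides it. The cost is protocol wording, a split CRF page and a few already scheduled visits for subjects off drug. It will not retain subjects who decline further contact, so the SAP still has to state how missing IGA is handled.
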